## 8.2. Laboratory Test Abnormalities

Laboratory abnormalities that constitute an AE in their own right (considered clinically meaningful, induce clinical signs or symptoms, require concomitant therapy, or require changes in study drug) should be recorded on the Adverse Event form in the eCRF. Whenever possible, a diagnosis rather than a symptom should be provided (eg, "anemia" instead of "low hemoglobin"). Laboratory abnormalities that meet the criteria for AEs should be followed until they have returned to normal or an adequate explanation of the abnormality is found. When an abnormal laboratory test result corresponds to a sign or symptom of a previously reported AE, it is not necessary to separately record the laboratory test result as an additional event.

Laboratory abnormalities that do not meet the definition of an AE should not be reported as AEs. A Grade 3 or 4 (severe) AE does not automatically indicate an SAE unless it meets the definition of serious, as defined in Section 8.3.1. A dose modification for the laboratory abnormality may be required (see Section 5.4) and should not contribute to the designation of a laboratory test abnormality as an SAE.

## 8.3. Serious Adverse Events

### 8.3.1. Definitions

An SAE is defined as an event that meets at least 1 of the following criteria:

- Is fatal or life-threatening.
- Requires inpatient hospitalization or prolongation of existing hospitalization, unless hospitalization is a result of:
  - A routine treatment or monitoring of the studied tumor type not associated with any deterioration in condition (ie, bone marrow biopsy for AML subjects)
  - An elective surgery or preplanned treatment for a pre-existing condition that is unrelated to the tumor type under study and has not worsened since signing the ICF.
  - A treatment on an emergency outpatient basis for an event not fulfilling any of the definitions of a SAE and not resulting in hospital admission.
  - Any social reasons and respite care, in the absence of any deterioration in the subject's general condition.
- Results in persistent or significant disability, incapacity, or a substantial disruption of a person's ability to conduct normal life functions.
- Constitutes a congenital anomaly or birth defect.
- Is considered to be an important medical event or a medically significant event that may not result in death, be immediately life-threatening, or require hospitalization but may be considered serious when, based on appropriate medical judgment, the event may jeopardize the subject or may require medical or surgical intervention to prevent one of the outcomes listed above.

### **8.3.2. Reporting**

Every SAE, regardless of suspected causality (eg, relationship to study drug(s) or study procedure or disease progression), occurring after the subject has signed the ICF through the last study visit (or 30 days after the last dose of study drug, whichever is later) must be reported to the sponsor (or designee) within **24 hours** of learning of its occurrence, unless otherwise specified by the Protocol. Any SAEs occurring more than 30 days after the last dose of study drug should be reported to the sponsor or its designee only if the investigator suspects a causal relationship to the study drug.

Information about all SAEs is collected and recorded on the Adverse Event form of the eCRF. The investigator must assess and record the causal relationship of each SAE to the study treatment.

The investigator must also complete the Incyte Serious Adverse Event Report Form, in English, and send the completed and signed form to the sponsor or designee within 24 hours of becoming aware of the SAE. The investigator must provide a causality assessment, that is, assess whether there is at least a reasonable possibility that the SAE is related to the study treatment: suspected (yes) or not suspected (no). Refer to the Incyte Reference Guide for Completing the Serious Adverse Event Report Form.

The contact information of the sponsor's study-specific representatives is listed in the investigator manual provided to each site. The original copy of the SAE Report Form and the confirmation sheet must be kept at the study site.

Investigational site personnel must report any new information regarding the SAE within 24 hours of becoming aware of the information in the same manner that the initial SAE Report Form was sent. Follow-up information is recorded on an amended or new SAE Report Form, with an indication that it is follow-up to the previously reported SAE and the date of the original report. The follow-up report should include information that was not provided on the previous SAE Report Form, such as the outcome of the event (eg, resolved or ongoing), treatment provided, action taken with study drug because of the SAE (eg, dose reduced, interrupted, or discontinued), or subject disposition (eg, continued or withdrew from study participation). Each recurrence, complication, or progression of the original event should be reported as follow-up to that event, regardless of when it occurs.

If the SAE is not documented in the IB for the study drug (new occurrence) and is thought to be related to the sponsor's study drug, the sponsor or its designee may urgently require further information from the investigator for reporting to health authorities. The sponsor or its designee may need to issue an Investigator Notification (IN) to inform all investigators involved in any study with the same drug that this SAE has been reported. Suspected Unexpected Serious Adverse Reactions (SUSARs) will be collected and reported to the competent authorities and relevant ethics committees in accordance with Directive 2001/20/EC, or as per national regulatory requirements in participating countries.

### **8.4. Emergency Unblinding of Treatment Assignment**

Not applicable.

## 8.5. Pregnancy

Pregnancy, in and of itself, is not regarded as an AE unless there is suspicion that study drug may have interfered with the effectiveness of a contraceptive medication or method. When a pregnancy has been confirmed in a subject during maternal or paternal exposure to study drug, the following procedures should be followed in order to ensure subject safety:

- The study drug must be discontinued immediately (female subjects only; see Section [5.4.7](#) for the maximum permitted duration of study drug interruption).
- The investigator must complete and submit the Incyte Clinical Trial Pregnancy form to the sponsor or its designee within **24 hours** of learning of the pregnancy.

Data on fetal outcome and breastfeeding are collected for regulatory reporting and drug safety evaluation. Follow-up should be conducted for each pregnancy to determine outcome, including spontaneous or voluntary termination, details of the birth, and the presence or absence of any birth defects, congenital abnormalities, or maternal and/or newborn complications, by following until the first well-baby visit. Pregnancy should be recorded on a Clinical Trial Pregnancy form and reported by the investigator to the sponsor or its designee. Pregnancy follow-up information should be recorded on the same form and should include an assessment of the possible causal relationship to the sponsor's study drug to any pregnancy outcome, as well as follow-up to the first well-baby visit or the duration specified in local regulations, whichever is later. Refer to the Incyte Reference Guide for Completing the Clinical Trial Pregnancy Form.

**Any SAE occurring during pregnancy must be recorded on the SAE report form and submitted to the sponsor or designee.**

## 8.6. Warnings and Precautions

Special warnings or precautions for the study drug, derived from safety information collected by the sponsor or its designee, are presented in the Investigator's Brochure ([IB](#)). Additional safety information collected between IB updates will be communicated in the form of Investigator Notifications (INs). Any important new safety information should be discussed with the subject during the study, as necessary. If new significant risks are identified, they will be added to the ICF.

## 8.7. Data Monitoring Committee

No independent Data Monitoring Committee is planned for this study. Decisions to continue the enrollment in subsequent dose level cohort, dose level to be tested, as well as number of subjects to be evaluated, will be made after the appropriate data are collected and reviewed by sponsor representatives (eg, medical monitor) and investigators or designees. The group of sponsor representatives and investigators or designees will convene regularly (eg, once weekly) or ad hoc for specific discussions. Meeting minutes will be documented.

An internal Data Safety Monitoring Board (iDSMB) will review safety data at regular intervals throughout the study. The frequency of meetings will be contingent upon enrollment and availability of safety data for analysis and review. Details regarding membership, roles, and responsibilities of the committee are specified in the iDSMB charter.

## 8.8. Product Complaints

The sponsor collects product complaints on study drugs and drug delivery systems used in clinical studies in order to ensure the safety of study participants, monitor quality, and facilitate process and product improvements.

All product complaints associated with material packaged, labeled, and released by the sponsor or its designee will be reported to the sponsor. All product complaints associated with other study material will be reported directly to the respective manufacturer.

The investigator or his/her designee is responsible for reporting a complete description of the product complaint via email or other written communication to the sponsor contact or respective manufacturer as noted in the packaging information. Any AE associated with a product complaint should be reported as described in Section 8.1.2 of this Protocol.

If the investigator is asked to return the product for investigation, he/she will return a copy of the product complaint communication with the product.

## 9. STATISTICS

### 9.1. Study Populations

The populations to be analyzed include the following:

- The full analysis set/safety population consists of subjects enrolled in the study who received at least 1 dose of study drug.
- The PK/█ population consists of all enrolled subjects who had PK/█ data.

### 9.2. Selection of Sample Size

Part 1 and Part 3 of the study will use a standard 3 + 3 dose-escalation design, and the sample size will depend on the frequency of DLTs and the number of dose-escalation cohorts before reaching the MTD. Approximately 3 to 6 subjects will be enrolled in each dose level. Using this design, the probability of dose escalation for various DLT rates is given in Table 11.

**Table 11: Probability of Dose Escalation by DLT Rate**

True DLT Rate	Probability of Dose Escalation
10%	90.6%
20%	70.9%
30%	49.4%
40%	30.9%
50%	17.2%
60%	8.2%

For Part 2, approximately 15 subjects will be enrolled for each expansion cohort. The evaluation of 15 subjects will provide a  $\geq 90\%$  chance of observing at least 1 toxicity with a true event rate of  $\geq 15\%$ .

For Part 4, for each of the combination cohorts (TG C1, TG D1, and TG E1), up to approximately 30 subjects will be enrolled. The evaluation of 30 subjects will provide approximately 90% chance of observing at least 1 toxicity with a true event rate of  $\geq 7\%$ .

### **9.3. Level of Significance**

This is an exploratory study and no formal statistical tests will be performed. Unless otherwise specified, all confidence intervals will be at the 95% confidence level.

### **9.4. Statistical Analyses**

All statistical analyses are exploratory in nature. Continuous variables will be summarized using means, medians, standard errors, minimums, and maximums. Categorical variables will be summarized using frequency counts and percentages.

#### **9.4.1. Efficacy Analyses**

For subjects with solid tumors, AML, and MDS, the proportion of subjects who meet the response criteria as appropriate for the tumor type will be summarized with descriptive statistics.

[REDACTED]

For MF subjects, changes and percentage changes of spleen volume from baseline to Week 12 [REDACTED] will be summarized descriptively.

[REDACTED]

[REDACTED]

[REDACTED]

#### **9.4.3. Safety Analyses**

##### **9.4.3.1. Adverse Events**

A treatment-emergent AE is any AE either reported for the first time or worsening of a pre-existing event after first dose of study drug. Analysis of AEs will be limited to treatment-emergent AEs, but data listings will include all AEs regardless of their timing to study drug administration. Adverse events will be tabulated by the MedDRA preferred term and system organ class. Severity of AEs will be based on the NCI CTCAE v4.03 using Grades 1 through 4.

The subset of AEs considered by the investigator to have a relationship to study drug will be considered to be treatment-related AEs. If the investigator does not specify the relationship of the AE to study drug, the AE will be considered treatment-related. The incidence of AEs and treatment-related AEs will be tabulated.

#### 9.4.3.2. Clinical Laboratory Tests

Laboratory test values outside the normal range will be assessed for severity based on the normal ranges for the clinical reference laboratory. The incidence of abnormal laboratory values and shift tables relative to baseline will be tabulated.

Laboratory data will be classified into Grades 1 through 4 using CTCAE v4.03. The following summaries will be produced for the laboratory data:

- Number and percentage of subjects with worst postbaseline CTCAE grade (regardless of baseline value). Each subject will be counted only for the worst grade observed postbaseline.
- Shift tables from baseline to the worst postbaseline value will be produced using CTCAE grade.
- For laboratory parameters where CTCAE grades are not defined, shift tables to the worst postbaseline value using the low/normal/high classifications based on laboratory reference ranges.

#### 9.4.3.3. Vital Signs

Descriptive statistics and mean change from baseline will be determined for vital signs (blood pressure, pulse, respiratory rate, and body temperature) at each assessment time. Vital sign results will be reviewed for clinically notable abnormalities (see [Table 12](#)), and subjects exhibiting clinically notable vital sign abnormalities will be listed. A value will be considered an "alert" value if it is outside the established range and shows a > 25% change from baseline.

**Table 12: Criteria for Clinically Notable Vital Sign Abnormalities**

Parameter	High Threshold	Low Threshold
Systolic blood pressure	> 155 mmHg	< 85 mmHg
Diastolic blood pressure	> 100 mmHg	< 40 mmHg
Pulse	> 100 bpm	< 45 bpm
Temperature	> 38°C	< 35.5°C
Respiratory rate	> 24/min	< 8/min

#### 9.4.3.4. Electrocardiograms

Descriptive statistics and mean change from baseline will be determined for each ECG parameter at each assessment time. Electrocardiogram results will be reviewed for clinically notable abnormalities according to predefined criteria ([Table 13](#)). Subjects exhibiting clinically notable ECG abnormalities will be listed.

**Table 13: Criteria for Clinically Notable Electrocardiogram Abnormalities**

Parameter	High Threshold	Low Threshold
QTcF	> 470 ms	< 295 ms
PR	> 220 ms	< 75 ms
QRS	> 120 ms	< 50 ms
QT	> 500 ms	< 300 ms
RR	> 1330 ms	< 600 ms

QTcF = Fridericia correction.

#### **9.4.3.5. Adverse Events of Special Interest**

Based on preclinical data generated to date, there is reason to believe that subjects will develop some level of thrombocytopenia. No human data have been generated yet to support this. Additionally, there is a chance for a "rebound" effect on platelets (potentially thrombocytosis) once the drug is discontinued, but human data have not been generated to support this effect. Subjects will be monitored closely and based on CTCAE grading of thrombosis will be reported as AEs as appropriate.

#### **9.4.4. Pharmacokinetic Analysis**

The PK parameters of  $C_{max}$ ,  $T_{max}$ ,  $C_{min}$ ,  $AUC_{0-t}$ ,  $t_{1/2}$ , and  $Cl/F$  (INCB059872) will be calculated from the blood plasma concentrations of INCB059872 using standard noncompartmental (model-independent) PK methods. Pharmacokinetic calculations will be performed, if appropriate, using commercial software such as WinNonlin®. Nominal times will be used in all cases, except when the difference between the actual time and nominal time is greater than 15 minutes for samples collected up to 4 hours after administration and greater than 30 minutes for samples collected more than 4 hours after administration; in these cases, actual time will be used for PK analysis. Refer to [Appendix C](#) for a detailed list and description of the PK parameters.

If there is a sufficient amount of plasma concentration data from this study, the data will be analyzed by standard population PK methods using appropriate software (eg, NONMEM).

[REDACTED]

[REDACTED]

[REDACTED]

#### **9.5. Analyses for the Data Monitoring Committee**

Preplanned analyses of safety will be provided to the iDSMB at regular intervals throughout the study as specified in the iDSMB charter.

#### **9.6. Interim Analysis**

In Part 4, a stopping rule for futility is planned for each combination dose expansion treatment group. The futility analyses for combination TGs will be conducted when 15 subjects for each disease type have been treated and evaluated for response or have permanently discontinued study treatment because of disease progression, withdrawal of consent, or death. The futility

analyses for TG D1 will be conducted when the first 15 subjects with AML or when the first 15 subjects with MDS have been treated. Combination TG C1 will be terminated for futility if  $\leq 1$  of the 15 subjects responded (ie, CR, CRi, MLFS) based on assessments provided by investigator. Combination TG D1 will terminate enrollment for subjects with AML if  $\leq 2$  of the first 15 AML subjects responded (ie, CR, CRi, MLFS) or will terminate enrollment for subjects with MDS if  $\leq 2$  of the first 15 MDS subjects responded (ie, CR or marrow CR), based on assessments provided by investigator. Combination TG E1 will be terminated for futility if  $\leq 1$  of the 15 subjects responded (ie, CR or PR) based on assessments provided by investigator.

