**Statistical Methods:**

Sample size consideration: Parts 1 and 3 of the study will use a 3 + 3 dose-escalation design, and the sample size will depend on the frequency of DLTs and the number of dose-escalation cohorts before reaching the MTD. For Part 2, up to approximately 15 subjects will be enrolled for each expansion cohort. The evaluation of 15 subjects will provide a  $\geq 90\%$  chance of observing at least 1 toxicity with a true event rate of  $\geq 15\%$ . For Part 4, for each of the combination cohorts (TG C1, TG D1, and TG E1) up to approximately 30 subjects will be enrolled. The evaluation of 30 subjects will provide approximately 90% chance of observing at least 1 toxicity with a true event rate of  $\geq 7\%$ .

All statistical analyses are exploratory in nature; descriptive statistics (eg, mean, standard deviation, range) will be derived where appropriate. The clinical safety data (vital signs, ECGs, laboratory tests, and AEs) will be descriptively summarized.

Pharmacokinetic [REDACTED] data will be analyzed. For subjects with solid tumor, AML, and MDS, the proportion of subjects who meet the response criteria as appropriate for the tumor type will be [REDACTED] summarized with descriptive statistics.

[REDACTED] For MF subjects, changes and percentage changes of spleen volume from baseline to Week 12 [REDACTED] will be summarized descriptively.

In Part 4, a stopping rule for futility is planned for each combination dose expansion treatment group. The futility analyses for combination TGs will be conducted when 15 subjects for each disease type have been treated and evaluated for response or have permanently discontinued study treatment because of disease progression, withdrawal of consent, or death. The futility analyses for TG D1 will be conducted when the first 15 subjects with AML or when the first 15 subjects with MDS have been treated and evaluated. Combination TG C1 will be terminated for futility if  $\leq 1$  of the 15 subjects responded (ie, CR, CRI, morphologic leukemia-free state [MLFS]) based on assessments provided by investigator.

Combination TG D1 will terminate enrollment for subjects with AML if  $\leq 2$  of the first 15 AML subjects respond (ie, CR, CRI, or MLFS), or will terminate enrollment for subjects with MDS if  $\leq 2$  of the first 15 MDS subjects responded (ie, CR or Marrow CR), based on assessments provided by investigator.

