#### **4.1.4. Combination Dose Expansion (Part 4)**

[figure not shown]
Upon identification of the recommended dose(s) for each treatment combination in Part 3, expansion cohorts of approximately 30 subjects in each treatment group may begin enrollment to further determine safety, tolerability, efficacy, PK, [REDACTED] of the selected dose(s).

- Combination TG C1: INCB059872 in combination with ATRA using the regimen identified in Part 3 in subjects with relapsed/refractory AML.
- Combination TG D1: INCB059872 in combination with azacitidine using the regimen identified in Part 3 in subjects with newly diagnosed, treatment-naive AML or MDS with at least 5% bone marrow blasts and IPSS-R intermediate or higher risk disease who are unfit to tolerate standard intensive chemotherapy at study entry and who are eligible to receive azacitidine as first-line therapy for the disease under study.
- Combination TG E1: INCB059872 in combination with nivolumab using the regimen identified in Part 3 in subjects with advanced SCLC who previously progressed on platinum based treatment.

In Part 4, a stopping rule for futility is planned for each combination dose expansion treatment group. The futility analyses for combination TGs will be conducted when 15 subjects for each disease type have been treated and evaluated for response or have permanently discontinued study treatment because of disease progression, withdrawal of consent, or death. The futility

analyses for TG D1 will be conducted when the first 15 subjects with AML or when the first 15 subjects with MDS have been treated.

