**Table 7: Schedule of Assessments (Continued)**

Procedure	Protocol Section	Screening	Treatment						EOT	Follow-Up		Notes	
			Cycle 1				Cycles 2+			Safety	Disease Status		
			Days -28 to -1	Day 1 (± 2 Days)	Day 8 (± 2 Days)	Day 15 (± 2 Days)	Day 22 (± 2 Days)	Day 1 (± 2 Days)	Day 15 (± 2 Days)				
AML/MDS disease assessments	7.6, 6.4.2	X						X*		X		X	* Every 4 weeks from baseline; can be peripheral blood or bone marrow aspirate or biopsy.
MF disease assessments (spleen palpation)	7.6, 6.4.2	X	X					X*		X		X	* Every 4 weeks from Week 4 through Week 24 and every 12 weeks after Week 24.
MF disease assessments (bone marrow assessment)	7.6	X						X*					* Every 24 weeks.
MF subjects: MRI of the upper and lower abdomen and pelvis	7.6	X						X*					* Every 12 weeks from baseline; CT scan may be substituted if MRI is contraindicated.
Review AEs	8.1	X	X	X	X	X	X	X	X	X	X		
Study drug dispensing	N/A		X				X*						* Drug dispensed on Day 1 of each cycle.

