Bone marrow examination (aspirate and biopsy) is required at screening for subjects with diseases that are typically monitored through bone marrow examination, including AML, MDS, and MF. Note: subjects with a history of allogenic hematopoietic stem cell transplantation should have bone marrow collected and analyzed locally for the purposes of determining disease status (where applicable); however their sample does not need to be processed for sequencing due to chimeric potential.

Data from the pathology report result from the bone marrow examination will be captured in the eCRF. All bone marrow examinations should include a unilateral aspiration and biopsy with FISH and cytogenetic testing, when feasible and indicated. Subjects may be enrolled based on a biopsy only when a "packed marrow" precludes aspiration at the decision of the medical monitor. Results of assessments performed under standard of care before the signing of informed consent may be used as the baseline disease assessment in lieu of a study-specific procedure if performed within 60 days of the first dose of study drug (Cycle 1 Day 1) and if adequate archive material is available and there has been no anticancer therapy in the interim.

For disease assessment timepoints in AML, MDS, and MF that do not correspond to a bone marrow examination, peripheral blood myeloid blast percentage will be evaluated by microscopic evaluation or other appropriate methodology and will be used as appropriate in conjunction with other parameters (eg, cytopenias) in determining disease status.

For AML and MDS subjects, a bone marrow disease assessment is strongly encouraged during Cycle 2, preferably at Cycle 2 Day 1 for subjects who have a significant circulating blast count reduction (as determined by the investigator), including subjects who are not completely cleared of circulating blasts; a bone marrow biopsy and/or aspirates for response is to be performed at Cycle 4 Day 1 or earlier as clinically indicated, followed by every other month as clinically indicated, or upon circulating blood cell recovery to assess antileukemic activity (cytogenetic testing is not required if CR is not presented). Bone marrow examination schedule can be modified with approval from the medical monitor.

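### The TG D1 futility look has two conflicting triggers, and for TG C1 and TG D1 neither trigger waits for the marrow that every counted response requires

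*Protocol*

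**What the plan says.** **Trigger.** The general sentence in Protocol 9.6 reads "The futility analyses for combination TGs will be conducted when 15 subjects for each disease type have been treated and evaluated for response", with permanent discontinuation for progression, withdrawal of consent or death as the alternative. The sentence specific to TG D1 follows, and there the look is made "when the first 15 subjects with AML or when the first 15 subjects with MDS have been treated". Section 4.1.4 and the Part 4 design text of the synopsis also stop at treatment. The Statistical Methods part of the synopsis says "when the first 15 subjects with AML or when the first 15 subjects with MDS have been treated and evaluated". SAP Sections 3 and 10.1 use the treated-and-evaluated form for every combination expansion group.

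**Boundary.** TG C1 stops if no more than 1 "of the 15 subjects responded (ie, CR, CRi, MLFS) based on assessments provided by investigator". TG D1 stops enrolment in a disease if no more than 2 of its first 15 subjects respond (AML: CR, CRi or MLFS; MDS: CR or marrow CR). SAP 10.2 fixes the analysis at exactly 15 subjects.

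**Assessments.** The Table 7 entry for AML/MDS is "Every 4 weeks from baseline; can be peripheral blood or bone marrow aspirate or biopsy". Section 7.6 adds that "a bone marrow biopsy and/or aspirates for response is to be performed at Cycle 4 Day 1 or earlier as clinically indicated". A Cycle 2 marrow is encouraged, not required, and only for subjects with a significant fall in circulating blasts. Appendices D and F define all the counted responses by marrow blasts.

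**The concern.** There are two gaps. First, the protocol gives two different moments for the same TG D1 decision. Read literally, 4.1.4 and 9.6 allow the look as soon as the 15th subject has been dosed. Second, agreeing on treated and evaluated would not be enough for TG C1 or TG D1. A subject with one blood-only assessment at Week 4 could be called evaluated although no counted response could yet have been documented.

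The boundaries are counts out of a fixed 15. No text says how an on-treatment subject with no post-baseline marrow is handled at the look. Counting that subject as a non-responder is an inference from the fixed denominator. It agrees with SAP 7.3.2.2.1 and 7.3.3.2.1, which keep inadequately assessed subjects in the response-rate denominator. On that basis the observed count is biased low, and enrolment to a combination that works could be closed on immature data.

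**Working it through.** **The plan's own figure.** The only Part 4 figure is about a 90% chance of seeing at least one toxicity in 30 subjects at a true rate of 7%: 1 − 0.93^30 = 0.887, which agrees. The documents give no operating characteristics for the futility boundaries, so there is no stated stopping probability to reproduce.

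**Inputs from the documents.** Boundary c = 2 of 15 (TG D1) and c = 1 of 15 (TG C1). Cycle 4 Day 1 falls 3 × 28 = 84 days after first dose. A blood-only assessment is possible at Day 28.

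**Assumptions.** Even accrual at 1 or 2 subjects per month of the disease concerned (a gap of 30.44 or 15.22 days); no marrow before Day 84; absence of a marrow unrelated to response; true rates of 40% (TG D1) and 20% (TG C1).

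**Step 1: how many of the 15 have had a marrow (m).** Number the subjects by how many enrolled after them, j = 0 to 14.
- Look at the 15th first dose: need j × gap ≥ 84. At 1 per month j ≥ 3, so m = 12. At 2 per month j ≥ 6, so m = 9.
- Look at the 15th subject's Day 28: need j × gap ≥ 56. At 1 per month j ≥ 2, so m = 13. At 2 per month j ≥ 4, so m = 11.

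**Step 2: probability of stopping.** The other 15 − m subjects cannot add a response, so P(stop) = Σ(k = 0 to c) C(m,k) p^k (1−p)^(m−k).

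TG D1, p = 0.40, c = 2:
- m = 15: 0.0005 + 0.0047 + 0.0219 = 0.027
- m = 13: 0.0013 + 0.0113 + 0.0453 = 0.058
- m = 12: 0.0022 + 0.0174 + 0.0639 = 0.083
- m = 11: 0.0036 + 0.0266 + 0.0887 = 0.119
- m = 9: 0.0101 + 0.0605 + 0.1612 = 0.232

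TG C1, p = 0.20, c = 1:
- m = 15: 0.0352 + 0.1319 = 0.167
- m = 13: 0.0550 + 0.1787 = 0.234
- m = 11: 0.0859 + 0.2362 = 0.322

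| Look | Group, true rate | All 15 assessable | 1 per month | 2 per month |
|---|---|---|---|---|
| 15th first dose | D1, 40% | 3% | 8% (m = 12) | 23% (m = 9) |
| 15th subject's Week 4 | D1, 40% | 3% | 6% (m = 13) | 12% (m = 11) |
| 15th subject's Week 4 | C1, 20% | 17% | 23% (m = 13) | 32% (m = 11) |

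TG C1 has no first-dose row because no document gives it that trigger.

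**Step 3: the other extreme.** If every subject had a marrow at Cycle 2 Day 1 (Day 28), the Week 4 look would have m = 15 and no inflation.

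**The case against.** - **The TG D1 sentence may only set the counting unit.** The sentence before it in 9.6 covers all combination groups and requires evaluation, and so does the SAP, which by its Section 2.1 stays in force for later amendments. On this view a first-dose look is the least natural reading. That is a fair point, and a reader should not infer that evaluation is required only in the synopsis. The contradiction in the text remains, and the reading does not settle what evaluation means.
- **Evaluated for response may already mean the marrow.** Section 7.6 describes blood at non-marrow visits as informing disease status and the marrow as the test for response. This is plausible, but no trigger text says it, and Table 7 lists blood alone as a disease assessment.
- **Early marrows are aimed at likely responders.** Section 7.6 encourages a Cycle 2 marrow after a blast reduction and allows one on blood count recovery. Subjects without a marrow are therefore more likely to be non-responders than the model assumes. This stands, and it makes the figures above upper bounds.
- **A stop costs little in TG D1.** About 30 places are shared by AML and MDS, so with a 15/15 split each look comes at or near full enrolment. This also stands. An early closure matters mainly when the split is uneven.
- **The study is exploratory, with safety as the primary endpoint.** True, but the rule still closes enrolment.

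Two stronger inferences fail. A wrong stop would not leave the response rate unestimated: the SAP still reports it with an exact 95% interval and pools each expansion group with its escalation group (5.2). Nor is the 27.8% CR/CRi rate in Protocol 1.3.2 a benchmark for an active combination. It is the azacitidine-alone rate and leaves out MLFS, which the protocol's rule counts.

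**Conclusion.** The concern holds in a limited form and should be fixed. The TG D1 trigger is contradictory within the protocol and between protocol and SAP. For both TG C1 and TG D1, nothing requires a subject to have had the marrow without which no counted response can be shown. The direction of the bias, toward stopping, follows from the fixed denominator of 15 if unassessed subjects are counted as non-responders, which the documents imply but do not state.

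The size is uncertain because accrual is not given. At 1 to 2 subjects per month, the Week 4 reading roughly doubles to quadruples a small stopping risk in TG D1 at a 40% rate, and adds about 7 to 16 percentage points in TG C1 at a 20% rate. The literal first-dose reading is worse and applies to TG D1 only. All of these are upper bounds, and the inflation at a Week 4 look vanishes if every subject has a Cycle 2 Day 1 marrow. The consequence of a wrong stop is a less precise response estimate from a smaller cohort.

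**What to change.** Use one trigger in the synopsis (both places), Protocol 4.1.4 and 9.6, and SAP Sections 3 and 10. For TG C1, and for each disease in TG D1, the look is made when each of the first 15 subjects has met one of these conditions:
- has had the protocol-scheduled post-baseline response marrow (Cycle 4 Day 1, or the replacement approved by the medical monitor, since 7.6 allows the schedule to be modified);
- has already documented a qualifying response;
- has permanently discontinued for a reason listed in 9.6. If other discontinuations, such as those for toxicity, are to count, reconcile that list.

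State that a blood-only assessment does not make an on-treatment subject evaluated for response. State also whether the 4-week minimum duration for MDS responses (Appendix F; SAP 7.3.3.2.1) applies at the look. The SAP is based on Amendment 5 and has a single TG D1 look, so it needs the by-disease wording as well.

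**Cost.** Text changes only, with no new procedure. The look comes up to about 12 weeks after the 15th first dose, and a few more subjects may enrol meanwhile unless enrolment is paused.
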